8.1 Definition of Protocol Deviations and Analysis Sets

Important protocol deviations are protocol deviations that might significantly affect the completeness, accuracy, and/or reliability of the study data or that might significantly affect a participant's rights, safety, or well-being.

For this study, important protocol deviations will be identified and confirmed at the protocol deviation review meetings.

8.2 Definition of Analysis Populations and Subgroups

The registry target population includes all subjects who participated in Sponsor oral cladribine Phase I to III clinical trials in MS associated with a protocol approved prior to the time of submission of the marketing application and completed (last patient, last visit) after November 2008. This corresponds to five clinical trials (protocol number/study name):

- 25643/CLARITY
- 26593/ONWARD
- 27820/CLARITY EXTENSION
- 27967/Pantoprazole DDI
- 28821/ORACLE MS

Subjects will be analyzed according to their actual exposure to oral cladribine. There will be no per-protocol analysis population excluding patients with protocol deviations.

Safety Analysis Population (SAF)

The Safety Analysis Population will consist of all subjects from studies CLARITY, CLARITY EXT, ORACLE MS and ONWARD who are enrolled in the PREMIERE registry as full participants.

Lymphocyte Analysis Population

The lymphocyte analysis population consists of all subjects from SAF with at least one absolute lymphocyte count (ALC) value in PREMIERE, with an associated ALC date after the end of clinical trial.

DDI Safety Set

The **DDI** Safety Set will include all subjects from the Pantoprazole DDI study who are enrolled in the PREMIERE registry as full participants. In this study, subjects received two single doses of 10 mg cladribine separated by a wash-out of at least 10 days and two 40 mg doses of pantoprazole on two consecutive days. Data from the DDI Safety Set will be presented in listings only.

9 General Specifications for Data Analyses

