*The efficacy and safety of cladribine tablets for the treatment of RRMS were investigated in a Merck Serono / EMD Serono-sponsored, Phase III, randomized, double-blind, 3-arm, placebo-controlled, multicenter study of 1326 subjects with RRMS (Study 25643, CLARITY). This trial provides the primary evidence of the efficacy and safety of oral cladribine in RRMS.*

*Data from clinical trials show that cladribine results in sustained and dose-related lymphopenia. In the CLARITY trial, the first 2 courses of oral cladribine resulted in decreases in mean absolute lymphocyte counts at Week 16 of 40% in the 3.5 mg/kg and 62% in the 5.25 mg/kg group. A partial recovery was observed by Week 48. Both cladribine dose groups were retreated with 2 courses of cladribine at Weeks 48 and 52. The nadir at Week 55 was comparable to that at Week 16 level in both treatment groups. The long-term effects of cladribine on hematopoiesis are unknown.*

*With regard to the risk of infections related to lymphopenia, in completed clinical trials, the risk ratio for herpetic infection was 1.98 (95%CI: 1.14-3.45). The risk ratio for infectious adverse events (AEs) and serious adverse events (SAEs) were 1.13 (95%CI: 1.01-1.26) and 1.56 (95%CI: 0.82-2.94), respectively.*

*Other delayed health effects including the possibility of an increased risk of malignancies are of interest and safety should therefore be monitored for a period extending beyond pharmacological exposure. The relative risk for any malignancy in placebo-controlled phases of completed clinical trials, was RR=2.31 (95%CI: 0.27 – 19.80). Although this point estimate suggests a two-fold increase in the risk of cancer among cladribine-exposed patients; the estimate is unstable as indicated by the wide 95% CI that contains 1. Malignancies were of various types and no lymphohematopoietic malignancies were observed.*

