## 6.3 Definitions related to study Endpoints

### Resolution of Persistent Lymphopenia

Subjects who complete or drop out of a cladribine clinical trial with a Grade 3 or Grade 4 lymphopenia as defined by the Common Terminology Criteria for Adverse Events (CTCAE) [8] will be defined as having ‘persistent lymphopenia’ and will be monitored until lymphopenia resolves. Resolution is the achievement of a CTCAE Grade 1 or Grade 0 lymphocyte count.

According to the CTCAE version 4.03 [8], lymphopenia grades are defined as follows:

- Grade 1: < lower limit of normal (LLN) to 800/mm^3 or < LLN to 0.8 × 10^9/L
- Grade 2: < 800–500/mm^3 or < 0.8–0.5 × 10^9/L
- Grade 3: < 500–200/mm^3 or < 0.5–0.2 × 10^9/L
- Grade 4: < 200/mm^3 or < 0.2 × 10^9/L

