## 8.4 Follow-Up Interviews

For MS subjects, the information to be ascertained in the follow-up interviews fall into five main categories:

- Updates in contact information
- Occurrence of SAEs (including time of event and outcome)
- Occurrence of AEs in the ‘Blood and Lymphatic System Disorders’ and ‘Neoplasms Benign, Malignant, and Unspecified’ SOCs (including time of event and outcome)
- Capture of any lymphocyte count assessments performed since last visit
- Prescription of immunosuppressant medications including type and start date

It is expected that subjects in PREMIERE will attend their routine MS care visits. The PRP is expected to request blood count and differential if lymphopenia has not resolved (i.e., lymphocyte count is equal or greater than  $0.8 \times 10^9/L$ ). All lymphocyte count results will be captured by the PRP regardless of monitoring frequency. Participating PRP will be instructed to have blood count and differential performed at least yearly until resolution of lymphopenia (i.e., a Grade 1 or Grade 0 lymphopenia), or end of the study period.

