6.2 Final Analysis

All final, planned analyses identified in the Clinical Study Protocol and in this IAP will be performed only after the last participant has completed the study (following protocol definition) with all study data in-house, all data queries resolved as much as possible, and the database locked.

7 Changes to the Planned Analyses in the Clinical Study Protocol

As usual, Statistical Analysis Plans are more detailed than relevant sections of the Study Protocols; such additions and refinements are therefore not mentioned in this section. Instead, only true deviations from statements in the study protocol are listed together with a brief rationale.

Table 1 Changes from the planned analyses in the clinical study protocol

Protocol Section: Item	Protocol definition	Changes implemented in the SAP
Section 5.6: Study Cohort	There will be no control/comparison group	"Never exposed to Cladribine" group will be considered as reference for a long-term non-treated population.

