15.1.4 Lymphopenia

Unless specified, reporting will be done for the Lymphocyte Analysis Population.

Evolution of absolute lymphocyte count (ALC) and specifically lymphopenia is of primary interest for treatment with cladribine.

ALC will be tabulated by grade using the NCI-CTCAE version v3.0, and lymphopenia grades are defined as follows:

Table 6 NCI-CTCAE Lymphopenia Grade

Laboratory Toxicity	Grade 1	Grade 2	Grade 3	Grade 4
ALC Decreased	<LLN – 800/mm ³ <LLN – 0.8 x 10 ⁹ /L	<800 – 500/mm ³ <0.8 – 0.5 x 10 ⁹ /L	<500 - 200/mm ³ <0.5 – 0.2 x 10 ⁹ /L	<200/mm ³ < 0.2 x 10 ⁹ /L

Change from first cladribine/placebo dose

Data collected from first cladribine/placebo dose [Study Day 1] to the last ALC value in PREMIERE will be presented and summarized on a continuous manner (change from Study Day 1 and absolute value) and by grade, over time.

ALC Study Baseline is defined by the latest ALC value prior or equal to first cladribine/placebo dose [Study Day 1].

Over-time target point will be presented using visit window computed relative to Study Day 1, as presented below.

In case multiple samples are collected in the same window, the value closest to the target day will be used for analysis, where the target day is the middle of the time window. If there are two values with the same time before and after the target day, the earlier (first) value will be used for analysis.

Table 7 Time window for lymphocyte from first cladribine/placebo dose

Evaluation	Target point (day)	Interval for analysis (Day)
ALC Study Baseline	Study Day 1	Last value prior to or equal to Study Day 1
Week 2	14	[2 ; 23]
Week 5	35	[24 ; 47]
Week 9	63	[48 ; 77]
Week 13	91	[78 ; 103]
Week 16	112	[104 ; 130]
Week 24	168	[131 ; 203]
Week 36	252	[204 ; 287]
Week 44	308	[288 ; 329]
Week 48	336	[330 ; 350]
Week 52	364	[351 ; 376]
Week 55	385	[377 ; 399]
Week 60	420	[400 ; 461]
Week 72	504	[462 ; 546]
Week 84	588	[547 ; 630]
Week 96	672	[631 ; 686]
Week 101	707	[687 ; 721]
Week 105	735	[722 ; 784]
Week 120	840	[785 ; 924]
Week 144	1008	[925 ; 1092]
Week 168	1176	[1093 ; 1260]
Week 192	1344	[1261 ; 1428]
Week 216	1512	[1429 ; 1596]
And every 24 weeks.... If needed		

Change from the end of clinical trial

A summary table of ALC similar to change from first cladribine/placebo dose will be presented.

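### Post-trial blood counts are called for only while lymphopenia is unresolved, so late ALC means and medians in the exposed group lean low and the never-exposed column is not a clean background

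*SAP*

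**What the plan says.** **When counts are taken.** Protocol 8.4: "The PRP is expected to request blood count and differential if lymphopenia has not resolved". It continues: "Participating PRP will be instructed to have blood count and differential performed at least yearly until resolution of lymphopenia", or until the end of the study period. There is no schedule for anyone else, only a capture rule: "All lymphocyte count results will be captured by the PRP regardless of monitoring frequency".

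**Who counts as persistently lymphopenic.** Protocol 6.3 applies the term to "Subjects who complete or drop out of a cladribine clinical trial with a Grade 3 or Grade 4 lymphopenia". This depends on grade, not on treatment. SAP 15.1.4 uses a wider notion of unresolved: no return to Grade 0 or 1 after a Grade 3 or 4 episode. A subject at Grade 2 at trial end after such an episode is therefore included.

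**Who is analysed.** SAP 8.2: "The lymphocyte analysis population consists of all subjects from SAF with at least one absolute lymphocyte count (ALC) value in PREMIERE", with a date after trial end.

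**What is tabulated.** SAP 15.1.4: "Data collected from first cladribine/placebo dose [Study Day 1] to the last ALC value in PREMIERE will be presented and summarized", as continuous values and by grade, in the Table 7 windows. A parallel summary from trial end uses the Table 8 windows.

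**The comparison.** In SAP section 7, Table 1, the never-exposed "group will be considered as reference for a long-term non-treated population". The example header in SAP 9.1 sets that column beside the exposed one.

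**The concern.** A subject's chance of having a count in a late window depends on the quantity being summarised. Once an exposed subject recovers, the instruction to test lapses; a subject who has not recovered stays under it. The tested subjects in a late window then over-represent those with low counts. Neither table is split by trial-end status or adjusted for who was tested.

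The rule does not name treatment, but it bears unequally on the two groups. Protocol section 3: "Data from clinical trials show that cladribine results in sustained and dose-related lymphopenia". Called-for tests will fall mainly on exposed subjects, while the never-exposed column after trial end rests mainly on routine-care tests.

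At stake is how the long-term lymphocyte course reads in the report. SAP 15.1.4 gives ALC evolution primary interest, and SAP section 7 replaces the planned life-table analysis of resolution with descriptive statistics, so the over-time tables will attract attention.

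**Working it through.** The plan states no testing rate and no prevalence of unresolved lymphopenia in the registry, so there is no figure of its own to reproduce. What follows is an illustration of mechanism and direction.

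**Inputs, all assumed**
- p = true share of exposed subjects unresolved in a late window: 5% (2% and 10% as range)
- a = chance of a count in that window if unresolved: 0.95
- b = chance of a count otherwise: 0.8, 0.5, 0.3, 0.15
- mean ALC: 0.6 if unresolved, 1.5 otherwise (×10⁹/L)
- among other subjects, being tested is unrelated to ALC

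**Formulas**
- Share unresolved among the tested: q = pa / [pa + (1−p)b]
- Mean among the tested: 0.6q + 1.5(1−q)
- Share with everyone in the denominator, as in SAP 9.13: pa
- Missing category: 1 − [pa + (1−p)b]
- Position of the tested median within the other subjects, if every unresolved value lies below it: (0.5−q)/(1−q)

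**Worked case**, p = 5%, b = 0.3: pa = 0.0475 and (1−p)b = 0.285, so q = 0.0475/0.3325 = 14.3%. The mean is 0.6×0.143 + 1.5×0.857 = 1.371. The missing category is 1 − 0.3325 = 67%.

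**Results for p = 5%** (true mean 0.05×0.6 + 0.95×1.5 = 1.455; true median at the 47th percentile of the others)

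| b | share among tested | mean among tested | median position | share, missing kept in | missing |
|---|---|---|---|---|---|
| 0.8 | 5.9% | 1.447 | 47th | 4.8% | 19% |
| 0.5 | 9.1% | 1.418 | 45th | 4.8% | 48% |
| 0.3 | 14.3% | 1.371 | 42nd | 4.8% | 67% |
| 0.15 | 25.0% | 1.275 | 33rd | 4.8% | 81% |

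Over the same values of b, the share among the tested runs from 2.4% to 11.4% for p = 2% and from 11.7% to 41.3% for p = 10%. If a = b, the share among the tested equals the true share and there is no bias.

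**Entry to the analysis set.** With six yearly chances of a count, a subject who is not unresolved enters with probability 1 − (1−b)⁶; an unresolved subject enters almost surely. A 5% share unresolved at trial end becomes 5.1% (b = 0.5), 5.6% (0.3), 7.8% (0.15) or 16.6% (0.05). Unless routine testing is rare, the at-least-one-count criterion does little by itself; the distortion comes from who is tested in each window. The criterion does, however, restrict the in-trial values of Table 7 to subjects who later had a registry count.

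**A related inconsistency.** In Protocol 8.4 the parenthesis explaining lymphopenia that has not resolved gives a count at or above 0.8×10⁹/L. Protocol 6.3 defines resolution as Grade 1 or 0, which is that same range. The two passages must be reconciled, since they determine who is under the testing instruction.

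**The case against.** The strongest reply is that the plan already handles persistence elsewhere and already shows who is missing.

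- **Grade tables.** A reader might infer that late grade distributions will overstate lasting lymphopenia. The default in SAP 9.13 keeps missing observations in the denominator as their own category. On that basis the unresolved percentage is slightly low in the illustration (4.8% against 5%). The objection stands. What remains is a missing category that merges recovered, never-lymphopenic and no-longer-followed subjects, and the temptation to read grades among the tested only.
- **Resolution endpoint.** A reader might infer that the time-to-resolution endpoint is biased in the same way. SAP 15.1.4 follows subjects unresolved at trial end to a resolved or unresolved outcome, and repeats this on the full safety population with the CRF tick box and resolution date. These analyses concern the subjects for whom counts are called for, and resolved subjects stay in the denominator. They are less affected, though the ALC-based version still needs a registry value. They do not correct the over-time tables.
- **Never-exposed sampling.** A reader might infer that never-exposed subjects with counts are chiefly those on disease-modifying drugs that need blood monitoring. No passage says so, and such testing could occur in both groups. The direction of any selection in that column is unknown.
- **Display.** SAP 9.13 already requires the number of non-missing values for continuous summaries, and SAP 10.1 reports the lymphocyte set against the safety population. That is part of what is needed; the number still in follow-up and the split by trial-end status are not there.
- **No inference; columns not specified.** SAP 9.14 plans no inference, and treatment columns for these tables are implied by the general header and the reference role rather than stated. Both are true, but descriptive means will still be compared side by side.

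**Conclusion.** The point holds in limited form. Testing depends on lymphocyte status by instruction, and SAP 15.1.4 summarises whoever was tested. Late-window means, medians and tested-only readings in the exposed group therefore tend to look too low. This direction assumes that unresolved subjects are tested more often than others and that routine testing of the others does not favour high counts.

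The size is unknown. With the assumed inputs and p = 5%, the mean is lowered by 0.008 (1.455 − 1.447) to 0.180 (1.455 − 1.275) ×10⁹/L; if routine testing was nearly complete, the effect is negligible. The never-exposed column after trial end is mainly a routine-care sample and should not be read as a clean background for these tables. The documents do not support saying that grade percentages are inflated or that the contrast between columns merely reflects who was tested. This is a worthwhile, inexpensive improvement in presentation.

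**What to change.** Amend SAP 15.1.4 as follows.

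1. Present the Table 8 windows, and the Table 7 values dated after each subject's own trial end, separately for subjects with unresolved lymphopenia at trial end and for all others. Use the SAP 15.1.4 definition, so that Grade 2 after a Grade 3 or 4 episode falls in the unresolved stratum.
2. In each window and treatment group, show number tested over number still in follow-up.
3. In the unresolved stratum, divide untested subjects into *previously documented resolved, not tested in this window* and *not tested*. This is a descriptive category only; no grade or value is carried forward, which respects the no-imputation rule in SAP 9.12.
4. Add a footnote that post-trial counts, including those in the never-exposed column, arise from status-driven or routine-care testing, and that persistence should be read from the resolution analyses.

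No further split by disease-modifying drug use is proposed; the cells would be too thin.

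**Cost.** SAP text and table shells only. The SAP records the last visit as already past, so sampling cannot change, and the inputs are already held. The price is more and smaller columns, with sparse cells for never-exposed subjects unresolved at trial end.

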9.1 Treatment groups

Analyses will be performed on the "as treated principle", where patients are allocated to the treatment group that they actually received in the clinical trial studies (which may be different from the study treatment to which they were randomized to).

Patients are assigned to the following treatment groups according to their actual treatment in one of the studies CLARITY alone, ONWARD, CLARITY/CLARITY EXTENSION, ORACLE MS, Pantoprazole DDI.

- **Never exposed to cladribine:** if a subject has taken only placebo (or placebo +IFN-β) in studies, then her/his data becomes part of the "Never exposed to cladribine" treatment group. A subject who switches treatment from placebo to cladribine in subsequent studies/periods **will not** be considered in this group.
- **Exposed to cladribine:** patients with at least one dose of cladribine. Subjects who were on placebo during the clinical trial and switched to cladribine in the extension study will contribute to the treatment group "Exposed to cladribine" from the moment they initiate cladribine.

An example of the header for table outputs is presented below.

Table 2 Table header example

	Never exposed to Cladribine (N=XXXX)	Exposed to Cladribine (N=XXXX)	Total (N=XXXX)
Safety Analysis Population	xxx (100.0)	xxx (100.0)	xxx (100.0)

9.2 Analysis Period

Analysis period for Safety Analysis Population and the DDI Safety Set

The analysis period for SAF and the DDI Safety Set is the time from the end of clinical trial + 1 day to the last date in PREMIERE.

Analysis period for Lymphocyte Analysis Population

Two analysis periods for lymphocyte analysis population are defined:

1. The time from first dose of cladribine/placebo* in clinical trials to the last absolute lymphocyte count (ALC) date with a value available in PREMIERE registry.
2. The time from first ALC date with a value in PREMIERE registry to the last ALC date with a value available in PREMIERE registry.

*** A subject who switches treatment from placebo to cladribine in subsequent studies/periods will be considered from first dose of cladribine and the placebo period will not be considered.**

9.3 Identification of patients

Patients are identified by their unique subject number taken from the subject ID in their first study. Other variables are created to distinguish their previous trial origin.

Table 3 Identification

Unique Subject Identifier (USUBJID)	First Previous Study Identifier	Last Previous Study Identifier (if diff)	Previous Clinical Trial
PPD [REDACTED]	PPD		CLARITY only
PPD [REDACTED]	PPD		ONWARD
PPD [REDACTED]	PPD	PPD	CLARITY/CLARITY EXTENSION
PPD [REDACTED]	PPD		Pantoprazole DDI
PPD [REDACTED]	PPD		ORACLE MS

9.4 Dictionary coding

The Adverse events (AEs) and Medical History will be coded to MedDRA version 21.0. Concomitant medications will be upgraded with WHO Drug Dictionary version March 2018 (WHODRUG B2 MARCH2018).

9.5 Study Day 1

Study Day 1 is the day of start of first study drug intervention (placebo or cladribine). For patients in the sequence placebo-cladribine, the placebo period is ignored and Study Day 1 is at the start of cladribine. The day before is Study Day -1 (no Study Day 0 is defined).

9.6 Registry Day 1

Registry Day 1 is defined as the end of clinical trial +1 day. The day before is Registry Day -1 (no Registry Day 0 is defined).

9.7 Baseline

Baseline is defined as registry baseline, which is the last assessment prior to or at Registry Day 1.

Unless specified, the demographics at baseline will be computed considering the last assessment prior to or at Registry Day 1.

9.8 End of clinical trial

The end of the clinical trial is defined as the last date of data collection from the last cladribine clinical trials.

9.9 Last date in PREMIERE

Last date in PREMIERE is the last date from any datasets including death and AE start date.

Programming rule to cover possible unclean data:

For subjects who died, last date in PREMIERE is the date of death and all data collected after date of death are ignored.

9.10 Last ALC date with value in PREMIERE

Last ALC date with an associated value (value not missing) in the PREMIERE registry is considered.

Programming rule to cover possible unclean data:

The last ALC date with value in PREMIERE is defined as the last ALC date with value after the end of clinical trial.

9.11 Conversion factors

Unless specified, the following conversion factors will be used to convert days into months or years:

- 1 year = 12 months = 365.25 days

9.12 Handling of missing data

Several attempts are to be made to contact subjects and to limit missing data (see protocol section 9.3.1). There will be no imputation for missing data.

9.13 Presentation of continuous and qualitative variables

Continuous and qualitative variables:

Continuous variables will be summarized using descriptive statistics, i.e.

- number of subjects (N),
- number of subjects with non-missing values,
- mean, standard deviation,
- median, 25th Percentile - 75th Percentile (Q1-Q3),
- minimum, and maximum.

Qualitative variables:

Qualitative variables will be summarized by counts and percentages. Unless otherwise stated, the calculation of proportions will be based on the number of subjects in the analysis set of interest. Therefore, counts of missing observations will be included in the denominator and presented as a separate category.

